8.5 Expedited Reporting of Events

Any study-related unanticipated problem posing risk to subjects or others, and any type of serious adverse event or unanticipated device reaction, will be reported to the IRB and funding sponsor within 24 hours of knowledge of the event. Investigators will use the appropriate SAE/UP CRF to record events and a line item will also be added to the AE log CRF.

The minimum necessary information to be provided at the time of the initial expedited event report includes:

- Study identifier
- Study Center
- Subject number
- A description of the event
- Date of onset
- Current status
- Whether study intervention was discontinued
- The reason why the event is classified as serious
- Investigator assessment of the association between the event and study intervention

8.5.1 Follow-up report

If an SAE, UP or Unanticipated Adverse Device Effect has not resolved at the time of the initial report and new information arises that changes the investigator's assessment of the event, a follow-up report including all relevant new or reassessed information (e.g., concomitant medication, medical history) should be submitted to the IRB. The investigator is responsible for ensuring that all events are followed until either resolved or stable.

8.5.2 Sponsor reporting: Notifying the Funding Sponsor

Electronic notification of any adverse events related to the use of the EnsoETM study device will be sent to the funding sponsor as determined by the principal investigator and study team.

8.6 Unblinding Procedures

The study team will not be blinded to the randomization assignment. The study team will be instructed to maintain blinding for participants until after their EGD unless a participant has a clinical need to know their randomization assignment. The decision to unblind will be at the discretion of the study PIs and only if unblinding would change clinical care. Unblinding for safety reasons will be recorded in study records and it will be reported to the IRB and the funding sponsor at the time of continuing review. Though we have found it hard to ensure participants stay blinded while in the hospital, we have instructed the extended care team to limit disclosure to the patient until after the EGD at the earliest. The EGD images will be de-identified and batch reviewed to ensure reviewers are not aware of the treatment arm, and all other endpoints are objective/quantitative and thus would not change based on blinding.

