3.1.3 Follow Up Visit (Day 30 -14/+30 days)

Follow up data will be collected at approximately 1 month following the ablation procedure. This is a standard of care follow up visits that typically occurs following an atrial fibrillation ablation procedure. The standard of care procedures that will be done at these visits include:

- Physical Exam
- Interim History and concomitant medication use
- Vital signs

In addition to the standard of care procedures, the research team will also collect the following:

- Adverse event information
- Atrial fibrillation recurrence

If a participant does not attend their routine 1 month clinical follow up, the research staff will attempt to contact the participant by phone to review their interim history, medication use and collect adverse event and atrial fibrillation recurrence information.

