3.2.3 Primary Safety Endpoints

All patients will undergo EGD following the procedure to evaluate the primary endpoint of esophageal thermal injury. We will also collect adverse events for all participants for 1 month following the ablation procedure.

4 Study Population and Duration of Participation

All patients will have met guideline recommendations for the AF ablation procedure and will have signed an informed consent for the clinical procedure.

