5.5 Blinding

Due to the nature of this study, the physicians will not be blinded to the randomization assignment, however participants will be blinded. Once a subject is randomized, the research team will receive the randomization assignment (EnsoETM or SOC) and proceed with the procedures per the assignment. In addition, the gastroenterologist interpreting the EGD study for the primary endpoint assessment will be blinded to the participants' randomization.

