8.2 Recording of Adverse Events

At each contact with the subject, the investigator will seek information on adverse events by specific questioning and, as appropriate, by examination. Information on all adverse events will be recorded immediately in the source document, and also in the appropriate adverse event case report form (CRF). All clearly related signs, symptoms, and clinically significant abnormal diagnostic procedures results should be recorded in the source document, though should be grouped under one diagnosis.

All adverse events occurring during the study period (consent through Visit 3 – 1 month follow up) will be recorded. The clinical course of each event will be followed until resolution, stabilization, or until it has been determined that the study intervention or participation is not the cause. Serious adverse events that are still ongoing at the end of the study period will be followed up to determine the final outcome. Any serious adverse event that occurs after the study period and is considered to be possibly related to the study intervention or study participation will be recorded and reported immediately.

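### Section 8.6 requires participant masking only until the EGD, but adverse events are sought by questioning up to Visit 3, so later symptom reports can depend on knowledge of the arm.

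*Combined protocol and SAP*

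**What the plan says.** The Study Summary describes the trial as blinded. Section 5.5 adds that "the physicians will not be blinded to the randomization assignment, however participants will be blinded" and gives no date or event at which participant masking ends.

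Section 8.6 supplies the detail. On staff: "The study team will not be blinded to the randomization assignment". On participants: "The study team will be instructed to maintain blinding for participants until after their EGD", with an exception for a clinical need to know. It concedes that masking has been difficult to keep up during the hospital stay, and then states: "we have instructed the extended care team to limit disclosure to the patient until after the EGD at the earliest". It closes by saying that EGD images are de-identified and reviewed in batches, and that the remaining endpoints are objective or quantitative, so that blinding would make no difference to them.

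Section 3.2.3, headed Primary Safety Endpoints, says: "We will also collect adverse events for all participants for 1 month following the ablation procedure". Section 8.2 gives the method: "At each contact with the subject, the investigator will seek information on adverse events by specific questioning", with examination where appropriate. If the one-month visit is missed, 3.1.3 says that "the research staff will attempt to contact the participant by phone to review their interim history, medication use and collect adverse event" and AF recurrence information. Section 3.1.4 has the same phone fallback for AF recurrence at 3, 6 and 12 months. The adverse-event definition in 8.1.2 covers symptoms and experiences as well as signs and illnesses.

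**The concern.** Participant masking protects outcomes that depend on what the participant says. In this trial the required masking covers the outcome that depends on it least, a lesion grade read from images by a blinded gastroenterologist. It may then lapse before most of the period in which participants are asked how they have felt.

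The reports most exposed are subjective ones, such as throat, swallowing or chest complaints. A participant who knows that the study device was used might report more of these. One who believes the device was protective might report less. The direction is open.

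The safety data are put to use. Section 7.3.3 makes continued enrollment depend on a review of device and EGD safety and tolerability after the first 10 subjects, and 8.7 adds reviews at 20 and 40. Section 11.1 states a belief that device risks resemble those of the standard probe. Apart from the EGD findings, the adverse events are the trial's evidence on that belief. Because the questioner knows the arm by design, the participant is the only party to the interview who could be masked.

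**Working it through.** The plan states no figure on this point, so there is none to reproduce. The check compares sections and does simple arithmetic on the visit windows.

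**Timing**
- End of required masking: after the EGD, Day 0 to Day 2 (3.1.2, 8.6).
- Visit 3: Day 30, window -14/+30 (3.1.3). Earliest 30 - 14 = Day 16; latest 30 + 30 = Day 60.
- Gap between the EGD and Visit 3: shortest 16 - 2 = 14 days; longest 60 - 0 = 60 days.
- At the nominal Day 30, the part of the adverse-event period after the EGD is 30 - 2 = 28 to 30 - 0 = 30 days, that is 28/30 = 93% to 30/30 = 100%.

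These are shares of calendar time, not of events. Adverse events are also assessed at Visits 1 and 2, and the documents do not show how complaints divide before and after the EGD.

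**The justification in 8.6 against each outcome**
- *EGD injury occurrence, grade and number.* Read blind from de-identified images, so participant knowledge has no evident route in. The justification holds.
- *Posterior wall ablation parameters and acute PV reconnection.* Recorded during the procedure under general anesthesia. They do not depend on participant reports.
- *Adverse events to one month.* These include symptoms (8.1.2) and are sought by questioning (8.2), by phone if the visit is missed (3.1.3). The justification does not hold for symptom reports.
- *AF recurrence.* Taken from the medical record, or from the participant by phone when a visit is missed (3.1.3, 3.1.4). The justification does not hold for the phone reports.

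**Size**
A numerical bias would need the rate of subjective complaints, the share of participants who learn their arm, and the change in reporting that follows. The documents give none of the three. For scale only, with 30 per arm and an assumed true complaint rate of 25% in each, the standard error of the between-arm difference is sqrt(2 × 0.25 × 0.75 / 30) = 0.112, or 11.2 percentage points. This describes sampling noise in such a comparison and says nothing about how large a reporting shift would be.

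**The case against.** Several objections stand and limit the point.

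- A reader might infer that 8.6 orders disclosure once the EGD is done. It does not. The instruction to the care team sets an earliest time, and some participants may stay masked for longer.
- A reader might call 5.5 and 8.6 contradictory. More exactly, 5.5 leaves the duration open and 8.6 fills it in, so the fault is incomplete cross-referencing.
- A reader might infer that a planned between-arm safety test is compromised. No such test is specified. Section 7 analyses the lesion score, and 7.3.3 speaks of an overall safety analysis. What is exposed is a descriptive comparison in a pilot with no power calculation.
- It is tempting to attach a number, for example a 10 to 15 point reporting shift. Against the standard error above that would be 10/11.2 = 0.9 to 15/11.2 = 1.3 standard errors. The result only restates the chosen shift, and it places the whole shift in one arm. Controls also have an esophageal temperature probe and an EGD, so awareness of instrumentation is not confined to the device arm.
- Longer participant masking leaves the questioners unmasked, and they also rate severity and relatedness.

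One further objection does not stand: that masking already leaks in hospital, so a longer instruction is pointless. An imperfect mask still lowers the share of participants who know their arm when questioned, and the longer instruction does no harm. None of the objections rescues the claim in 8.6 that all the other endpoints are unaffected.

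**Conclusion.** The point holds in limited form. Required masking may lapse 14 to 60 days before Visit 3, and the reason given for that limit does not fit adverse events obtained by questioning or AF recurrence obtained by phone. Symptom reports after the EGD can depend on knowledge of the arm. That some do is not shown.

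The primary EGD endpoint is not touched, and no tested hypothesis is at risk. The direction and size of any effect on the safety comparison cannot be estimated from the documents. The conclusion assumes only that some participants learn their arm after the EGD and that some complaints are subjective. Section 8.6's own account of the hospital stay makes the first plausible. The change is worth making because it is cheap, not because a bias of known size has been demonstrated.

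**What to change.** 1. In 8.6, replace the EGD as the end of required participant masking with completion of the Visit 3 adverse-event assessment. Keep the clinical-need exception and give the extended care team the same instruction.
2. In 5.5 and the Study Summary, state who is masked and until when, in agreement with 8.6.
3. In 8.6, correct the closing justification to say that adverse events and AF recurrence obtained by interview may be affected by knowledge of the arm. This correction is needed even if the EGD cut-off is kept. It matters most for the 3, 6 and 12 month calls, which required masking to Visit 3 would not cover in full.
4. At Visit 3, record whether, when and why the participant learned the arm, and report this by arm as a description of how well masking held. Do not split the adverse-event table by this answer. It arises after randomization, and an adverse event can itself cause unblinding through the clinical-need exception, so a split table could create the association it is meant to detect.

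The cost is a few lines of text in three places, a revised care-team instruction, a short CRF item and one descriptive summary. Participants wait about a month to learn their arm, up to Day 60 at the end of the window, and some will learn it earlier. Because staff remain unmasked, the bias is reduced, not removed.

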8.7 Data and Safety Monitoring

It is the responsibility of the Principal Investigator to oversee the safety of the study. The Principal Investigator and designated members of the study team will be responsible for monitoring subject safety and applicable reporting to the IRB and study sponsor. This safety monitoring will include careful assessment of eligibility and detailed assessment and appropriate reporting of adverse events as noted above. Grading of EGDs will be done by a single physician contracted to perform the reads. Data collected on the study will be reviewed after 10 people are enrolled in the study. Another data review will occur at 20 and 40 patients enrolled.

9 Study Administration, Data Handling and Record Keeping

9.1 Confidentiality

Information about study subjects will be kept confidential and managed according to the requirements of the Health Insurance Portability and Accountability Act of 1996 (HIPAA). Those regulations require a signed subject authorization informing the subject of the following:

- What protected health information (PHI) will be collected from subjects in this study
- Who will have access to that information and why
- Who will use or disclose that information

- The rights of a research subject to revoke their authorization for use of their PHI.

In the event that a subject revokes authorization to collect or use PHI, the investigator, by regulation, retains the ability to use all information collected prior to the revocation of subject authorization. For subjects that have revoked authorization to collect or use PHI, attempts should be made to obtain permission to collect at least vital status (i.e. that the subject is alive) at the end of their scheduled study period.

9.2 Data Collection and Management

Data will be collected by trained research staff using source documents and CRFs. Source and CRFs will be entered into a RedCap data management system (DMS). Participants will be assigned a Participant ID "PID" for use on CRF data collection in for entry into the DMS to protect and ensure confidentiality.

Source data is all information, original records of clinical findings, observations, or other activities in a clinical trial necessary for the reconstruction and evaluation of the trial. Source data are contained in source documents. Examples of these original documents, and data records include: hospital records, clinical and office charts, laboratory notes, memoranda, subjects' diaries or evaluation checklists, pharmacy dispensing records, recorded data from automated instruments, copies or transcriptions certified after verification as being accurate and complete, microfiches, photographic negatives, microfilm or magnetic media, x-rays, subject files, and records kept at the pharmacy, at the laboratories, and at medico-technical departments involved in the clinical trial.

The study case report form (CRF) is the primary data collection instrument for the study. All data requested on the CRF must be recorded. All missing data must be explained. If a space on the CRF is left blank because the procedure was not done or the question was not asked, write "N/D". If the item is not applicable to the individual case, write "N/A". All entries should be printed legibly in black ink. If any entry error has been made, to correct such an error, draw a single straight line through the incorrect entry and enter the correct data above it. All such changes must be initialed and dated. DO NOT ERASE OR WHITE OUT ERRORS. For clarification of illegible or uncertain entries, print the clarification above the item, then initial and date it.

The study data will be stored indefinitely. A de-identified data set may be shared with the funding sponsor.

9.3 Records Retention

Study records, including administrative and participant related source and CRFs, will be retained for 7 years after the completion of the research (often marked by a final progress report).

10 Study Monitoring, Auditing, and Inspecting

10.1 Study Monitoring Plan

The investigator and research team will allocate adequate time for such monitoring activities. The Investigator will also ensure that the monitor or other compliance or quality assurance reviewer is given access to all the above noted study-related documents and study related facilities (e.g. clinical EP laboratories), and has adequate space to conduct the monitoring visit.

10.2 Auditing and Inspecting

The investigator will permit study-related monitoring, audits, and inspections by the IRB, government regulatory bodies, and University compliance and quality assurance groups of all study related documents (e.g. source documents, regulatory documents, data collection instruments, study data etc.). The investigator will ensure the capability for inspections of applicable study-related facilities.

Participation as an investigator in this study implies acceptance of potential inspection by government regulatory authorities and applicable University compliance and quality assurance offices.

11 Ethical Considerations

This study is to be conducted in accordance with applicable US government regulations and international standards of Good Clinical Practice, and applicable institutional research policies and procedures.

This protocol and any amendments will be submitted to a properly constituted Institutional Review Board (IRB), in agreement with local legal prescriptions, for formal approval of the study conduct. The decision of the IRB concerning the conduct of the study will be made in writing to the investigator and a copy of this decision will be provided to the funding sponsor before commencement of this study if required. The formal consent of a subject, using the IRB-approved consent form, must be obtained before that subject undergoes any study procedure. The consent form must be signed by the subject or legally acceptable surrogate, and the appropriately delegated research staff obtaining the consent.

11.1 Risks

Risks of the ablation procedure will be explained using the clinical procedure consent.

Additional risks of the study procedures are described below:

EnsoETM device risks: Placement of the EnsoETM device, similar to any device in the esophagus, can result in or exacerbate esophageal tissue damage, particularly in patients with known esophageal deformity or evidence of esophageal trauma. We believe these risks are similar to those whom receive the standard of care temperature monitor probes inserted into the esophagus during routine clinical procedures.

EGD procedure risks: Diagnostic upper endoscopy procedures are considered very safe and rarely can result in complications including bleeding, infection, and/or perforation. Large studies have reported the occurrence of any adverse event anywhere from 1 in 200 to 1 in 10,000 patients with major complications or death extraordinarily rare⁸.

Loss of Confidentiality Risks: there is the potential for loss of confidentiality during data collection.

11.2 Benefits

There are no known direct benefits to the participants in this study. There may be a benefit to cooling the esophagus to reduce or prevent damage during the ablation procedure. The knowledge gained by participation in this study may benefit society as a whole in the future and potentially lead to additional studies.

11.3 Risk Benefit Assessment

The risks of participating in the study are outweighed by the potential benefits of participating in the study.

11.4 Informed Consent Process / HIPAA Authorization

Participants will be provided an IRB approved consent form describing this study and providing sufficient information for subjects to make an informed decision about their participation in this study. A verbal review of the consent form will take place with the participant and delegated personnel. This consent form will include HIPAA authorization language which will also be reviewed with the participant. The formal consent of a subject, using the IRB-approved consent form, will be obtained before that subject undergoes any study procedure. The consent form must be signed by the subject or legally acceptable surrogate, and the investigator-designated research professional obtaining the consent. The participant will be consented in a private clinical space and will be given ample time to ask questions and have questions answered. As the majority of the procedures that will occur are standard of care, we will clearly discuss what the research part of the day and days after will include. The voluntary nature of the study will be reviewed and participants will be told that should they choose not to consent, their clinical care will not be effected.

12 Study Finances

12.1 Funding Source

This study is financed through a contract with Attune Medical. Attune Medical is considered the funding sponsor who will provide financial support to conduct the study and the EnsoETM device free of charge.

12.2 Conflict of Interest

All University of Pennsylvania Investigators will follow the University of Pennsylvania [Policy on Conflicts of Interest Related to Research](#).

